## 1. INTRODUCTION

### 1.1 MEDICAL BACKGROUND

Rheumatoid arthritis (RA) is a chronic systemic inflammatory disorder characterized by synovial inflammation in the joints and consequently, progressive joint destruction. Depending on the severity of the disease, systemic manifestations may occur including lung, cardiovascular, hematologic and ocular effects. If left untreated, RA may lead to severe functional disabilities, and therefore a considerable reduction in quality of life for the patient ([R11-4384](#), [R11-4383](#)). The prevalence of RA varies with factors such as gender, race and smoking status and is approximately 0.5% to 1% ([R07-0637](#)).

The cytokine tumor necrosis factor (TNF)-alpha is involved in inflammatory and immune responses. Elevated levels of TNF-alpha are found in the synovial fluid of RA patients, including juvenile idiopathic arthritis and psoriatic arthritis patients and it has been demonstrated that TNF-alpha (hereafter also referred to as TNF) plays a crucial role in both the pathologic inflammation and the joint destruction characteristic of these diseases. Thus, TNF targeted therapy plays an important role in RA through a reduction in the TNF-mediated downstream effects on other cell types involved in the inflammatory response.

There are five anti-TNF drugs that have been approved by the United States (US) Food and Drug Administration (FDA) and the European Medicines Agency (EMA) to treat moderate to severe RA that has not responded to one or more of the traditional disease-modifying antirheumatic drugs (DMARDs). These currently approved therapies include: adalimumab, etanercept, infliximab, certolizumab pegol, and golimumab. Efficacy has been demonstrated in all five therapies, in combination with methotrexate (MTX), by greater American College of Rheumatology 20%/50%/70% (ACR20/50/70) responses, an improvement in Disease Activity Score in 28 joints (DAS28), less radiographic progression, and an improvement in quality of life (Health Assessment Questionnaire – Disability Index [HAQ-DI], 36-item Short Form Health Survey version 2 [SF-36 v2]) ([R12-2515](#)).

### 1.2 DRUG PROFILE

BI 695501 is a monoclonal antibody being developed as a proposed biosimilar to the TNF-alpha blocker, adalimumab (US-licensed Humira® and EU-approved Humira®). Adalimumab is a recombinant human monoclonal immunoglobulin (Ig) G1 antibody specific to human TNF-alpha. It has human-derived heavy and light chain variable regions and human IgG1:k constant regions and is produced in a mammalian expression system ([R15-0739](#) and [R15-3225](#)).

Humira® binds specifically to TNF-alpha (and not TNF-beta) and blocks its interaction with the p55 and p75 cell surface TNF receptors. Humira® has also been shown to lyse cells expressing surface TNF in vitro in the presence of complement and modulate biological responses that are induced or regulated by TNF, including changes in adhesion molecules responsible for leukocyte migration (endothelial leukocyte adhesion molecule-1, vascular cell adhesion molecule-1, and intercellular adhesion molecule-1) (R15-0739).

After subcutaneous (SC) administration of a single 40 mg dose in healthy adult subjects, peak serum concentrations of Humira® are reached approximately 5 days after administration. The average absolute bioavailability of Humira® estimated from three studies following a single 40 mg SC dose was 64%. Following SC administration of 40 mg of Humira® every second week in adult RA patients, the mean steady-state trough concentrations were approximately 5 µg/mL (without concomitant MTX) and 8 to 9 µg/mL (with concomitant MTX), respectively. The serum Humira® trough levels at steady-state increased roughly proportionally with dose following 20, 40 and 80 mg SC dosing every other week and every week ([R15-0739](#) and [R15-3225](#)).

Population pharmacokinetic (PPK) analyses showed a trend toward higher apparent clearance of Humira® with increasing body weight. After adjustment for weight differences, gender and age appeared to have a minimal effect on Humira® clearance ([R15-0739](#) and [R15-3225](#)).

Humira® was evaluated in over 3000 patients in all RA trials that were performed prior to approval, with some patients treated for up to 60 months duration. In the EMA label, five randomized, double-blind and well-controlled studies were reported for Humira®, which assessed the efficacy and safety of Humira® for the treatment of RA ([R15-3225](#)).

In two of the five studies, long-term administration of Humira® was evaluated; patients received Humira® for  $\geq 52$  weeks.

In one study, 114 patients were enrolled to the open-label study and continued to receive Humira® 40 mg every other week for 60 months. Of these patients 86, 72 and 41 patients had ACR20, ACR50 and ACR70 responses, respectively, at Month 60 ([R15-3225](#)).

In a trial of 799 MTX-naïve, adult patients with moderate to severe active early RA, 42.9% of patients who received Humira®/MTX combination therapy achieved clinical remission (DAS28 <2.6) at Week 52 compared to 20.6% and 23.4% of patients receiving MTX monotherapy and Humira® monotherapy, respectively. Humira®/MTX combination therapy was clinically and statistically superior to MTX ( $p < 0.001$ ) and Humira® monotherapy ( $p < 0.001$ ) in achieving a low disease state ([R15-0739](#) and [R15-3225](#)).

In addition, it has been shown that individual components of the American College of Rheumatology (ACR) response criteria (number of tender and swollen joints, physician and patient assessment of disease activity and pain, and disability index scores) improved at 24 or 26 weeks compared to placebo ([R15-0739](#) and [R15-3225](#)).

Humira® treatment in RA patients has been associated with a decrease in levels of acute phase reactants of inflammation, C-reactive protein (CRP) and erythrocyte sedimentation rate (ESR), and serum cytokines (interleukin-6), compared to Baseline. Serum levels of the matrix metalloproteinases (MMP)-1 and MMP-3 that induce the tissue remodelling responsible for cartilage destruction were also decreased and patients experienced improvement in hematological signs of chronic inflammation after Humira® administration ([R15-3225](#)).

In addition to the analytical and pharmacological assays, the similarity between BI 695501 and US-licensed Humira® was assessed in a single-dose pharmacokinetic (PK) study in the cynomolgus monkey and a local tolerance study in rabbits. Additionally, the three-way PK similarity between BI 695501, US-licensed Humira® and EU-approved Humira® was demonstrated in a Phase I clinical study in healthy volunteers. The results of these studies are provided in the Investigator's Brochure (IB).

For a more detailed description of the drug profile, refer to the current IB which is included in the Investigator Site File (ISF).

## 2. RATIONALE, OBJECTIVES, AND BENEFIT - RISK ASSESSMENT

### 2.1 RATIONALE FOR PERFORMING THE TRIAL

Adalimumab (Humira®) has received regulatory approval for treatment of patients with RA in the US, the EU, and many other countries ([R15-0739](#) and [R15-3225](#)). BI 695501 is being developed as a proposed biosimilar to US-licensed Humira® and EU-approved Humira®.

This trial will be conducted in compliance with the Clinical Trial Protocol (CTP), the International Conference on Harmonisation (ICH) guidelines, Good Clinical Practice (GCP) and with all applicable and current regulatory requirements.

The rationale for conducting this trial is to generate long-term safety, efficacy, and immunogenicity data for the administration of the proposed biosimilar BI 695501 in patients with RA. This is a 1-year extension trial to Trial 1297.2, in which patient will have received 48 weeks of treatment with US-licensed Humira® or BI 695501, or with US-licensed Humira® for 24 weeks then BI 695501 for 24 weeks.

### 2.2 TRIAL OBJECTIVES

The objective of this trial is to provide long-term safety, efficacy, PK, and immunogenicity data on BI 695501 administered via prefilled syringe in patients with RA who have completed Trial 1297.2.

### 2.3 BENEFIT - RISK ASSESSMENT

Patient risk will be minimized in this trial by implementing conservative eligibility criteria. Due consideration has been given to previous experience with US-licensed Humira® and EU-approved Humira® in RA patients and side effect management advice (e.g., for hypersensitivity reactions) is provided for in this CTP. All trial personnel are directed to the BI 695501 IB for a description of the non-clinical and clinical experience with BI 695501. To date, a total of 175 healthy male volunteers (includes data from Trial 1297.8 and Trial 1297.1) have received BI 695501. As of 01 July 2015, 465 patients were included in Trial 1297.2.

Representatives from Boehringer Ingelheim (BI) and Safety, Clinical and Quality functions will review accumulating safety data at the monthly Medical and Quality Review Meeting.

Given the progressive nature of the disease, each patient will receive active RA treatment throughout the trial.

Patients will be carefully monitored during ambulatory (outpatient) visits for any safety signs and symptoms that may occur or arise following trial treatment. Adverse events (AEs), body temperature, vital signs, electrocardiograms (ECGs) and safety laboratory assessments as

well as immunogenicity data will be collected throughout the trial; therefore monitoring patients for safety outcomes over a prolonged period of time will be possible.

A potential for drug-induced liver injury (DILI, a rare event) is under constant surveillance by sponsors and regulators. Therefore, timely detection, evaluation, and follow-up of alterations of selected liver laboratory parameters to ensure patients' safety will be performed in this trial (see [Section 5.3.6](#)).

In addition, hypersensitivity reactions, anaphylaxis, and serious infections are considered adverse events of special interest (AESI), see Section 5.3.6.

In patients treated with Humira®, common adverse reactions reported in greater than 10% of patients include infections (e.g., upper respiratory tract infections, sinus infections), injection site reactions, headache and rash. Allergic reactions (e.g., allergic rash, anaphylactic reaction, fixed drug reaction, non-specified drug reaction, urticaria) have been observed in approximately 1% of patients ([R15-0739](#) and [R15-3225](#)).

Cases of hepatitis B virus (HBV) reactivation have been reported in patients receiving anti-TNF therapy. Some cases have been fatal, the majority of which were in patients concomitantly receiving other immunosuppressive medications. Carriers of HBV and patients with a history of HBV infection will be excluded from the trial.

Tuberculosis (TB) reactivation or new TB infections have been observed in patients receiving Humira® and other TNF-inhibitors, including patients who had previously received treatment for latent or active TB. Patients will be evaluated for TB risk factors and tested for latent infection prior to and during the trial due to the increased risk of opportunistic infections with Humira®.

In the controlled portions of clinical trials of some TNF-inhibitors, including Humira®, more cases of malignancies have been observed among TNF-inhibitor-treated adult patients compared to control-treated adult patients. Therefore, the possible risk for the development of malignancies cannot be excluded.

Further information regarding relevant contraindications, special precautions, adverse reactions and other recommendations for the use of US-licensed Humira® and EU-approved Humira® in RA patients are described in the prescribing information ([R15-0739](#) and [R15-3225](#)).

BI 695501, as a proposed biosimilar product, is expected to provide comparable efficacy, safety, tolerability and immunogenicity in patients with RA and therefore is expected to provide a similar benefit-risk profile as US-licensed Humira® and EU-approved Humira®.

An Independent Data Monitoring Committee (IDMC) is monitoring the 1297.2 trial and an IDMC safety review will be completed prior to the first patient's enrolment in the extension trial.

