**FLOW CHART**

| Visit   | 1                      | 2        | 3              | 4  | 5               | 6   | 7               | 8               | 9                      | 10        |
|---|------------------------|----------|----------------|----|-----------------|-----|-----------------|-----------------|------------------------|-----------|
| Week  | Screening  | Baseline | 6  | 12 | 18  | 24  | 32  | 40  | 48
EoT  | 58
SFU |
| Day   | -14                    | 1        | 43             | 85 | 127             | 169 | 225             | 281             | 337                    | 407       |
| Permitted visit window (days)   | ±3                     | ±1       | -              | ±2 | -               | ±2  | -               | -               | ±2                     | ±2        |
| Informed consent  | X                      |          |                |    |                 |     |                 |                 |                        |           |
| Assessment of eligibility   | X                      |          |                |    |                 |     |                 |                 |                        |           |
| Self-administration evaluation                              | X                      |          |                |    |                 |     |                 |                 |                        |           |
| Demographics  | X                      |          |                |    |                 |     |                 |                 |                        |           |
| LABS/SAFETY ASSESSMENTS  |                        |          |                |    |                 |     |                 |                 |                        |           |
| Infection screen: Hepatitis B (HbsAg); HCV and optional HIV test        | X                      |          |                |    |                 |     |                 |                 |                        |           |
| RF and anti-CCP antibodies  |                        | X        |                |    |                 |     |                 |                 | X                      |           |
| TB test   | X                      |          |                |    |                 |     |                 |                 | X                      |           |

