### **3.3.3 Exclusion criteria**

1. Patients who experienced Investigator-reported drug-related serious adverse events (SAEs) in Trial 1297.2.
2. ACR functional Class IV (see [Appendix 10.1](#)) or wheelchair/bed bound.
3. Primary or secondary immunodeficiency (history of, or currently active).
4. Positive QuantiFERON test.

5. Known clinically significant coronary artery disease or significant cardiac arrhythmias or severe congestive heart failure (New York Heart Association Classes III or IV), or interstitial lung disease observed on chest X-ray.
6. Anaphylactic reaction or hypersensitivity to adalimumab received in Trial 1297.2.
7. History or recent evidence of cancer including solid tumors, hematologic malignancies, and carcinoma in situ (except participants with previous resected and cured basal or squamous cell carcinoma, treated cervical dysplasia, or treated in situ Grade I cervical cancer within 5 years prior to the Screening Visit).
8. Positive serology for HBV or hepatitis C virus (HCV).
9. Patients who are expecting to receive any live virus or bacterial vaccinations during the trial, or up to 3 months after the last dose of trial drug.
10. Any treatment (including biologic therapies) that, in the opinion of the Investigator, may place the patient at unacceptable risk during the trial.
11. Patients with a significant disease other than RA and/or a significant uncontrolled disease (such as, but not limited to, nervous system, renal, hepatic, endocrine, or gastrointestinal disorders). A significant disease is defined as a disease which, in the opinion of the Investigator, may (i) put the patient at risk because of participation in the trial, or (ii) influence the results of the trial, or (iii) cause concern regarding the patient's ability to participate in the trial.
12. Premenopausal (last menstruation 1 year prior to screening), sexually active women who are pregnant or nursing, or are of child-bearing potential and not practicing an acceptable method of birth control, or do not plan to continue practicing an acceptable method of birth control throughout the trial (acceptable methods of birth control are intrauterine devices, surgical sterilization, double barrier, or vasectomized partner).

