### 5.3.3 Safety laboratory parameters

Blood and urine samples for determination of serum chemistry, hematology and urinalysis will be taken at the times indicated in the [Flow Chart](#).

The following laboratory parameters will be measured:

- Serum chemistry: creatinine, alkaline phosphatase, AST, ALT, gamma glutamyl transpeptidase, bilirubin (total and direct), glucose, total cholesterol, total protein, albumin, sodium, potassium, chloride, calcium

- Hematology: hemoglobin, hematocrit, platelets, white blood cells, lymphocytes, neutrophils
- Urinalysis: protein, glucose, blood

In addition, the following parameters will be analyzed at the visits indicated in the [Flow Chart](#):

- Infection screen: patients must have a negative serological test for hepatitis B surface antigen (HBsAg), for hepatitis C serology
- HIV screen (at the discretion of the Investigator where clinically indicated, and per local regulations)
- TB test (QuantiFERON® Gold assay)
- ESR and CRP
- Pregnancy testing for females of child-bearing potential only (serum human chorionic gonadotropin or urine)
- ADAs and nADAs

Rheumatoid factor (RF) and anti-cyclic citrullinated peptide (anti-CCP) antibodies will be analyzed at Baseline (Day 1) and Week 48.

The Investigator must assess all laboratory results. The Investigator will evaluate any change in laboratory values and all clinical laboratory tests will be reviewed for potential clinical significance at all time points throughout the trial. The Investigator should endeavor to provide a reason for all results deemed not clinically significant. If the Investigator determines a laboratory abnormality to be clinically significant, it will be considered an AE/SAE (see [Section 5.3.6](#)); however, if the laboratory value abnormality is consistent with a current diagnosis, it will be documented accordingly.

Blood samples will be analyzed by a central laboratory (except ESR). The central laboratory provider will also provide the materials for blood sampling. Instructions for the labelling, storage and shipment of the samples can be found in the Laboratory Manual. Details of all blood variable units and reference ranges can be found in the Laboratory Manual.

Pregnancy testing will be performed by a central laboratory using serum at Screening or local laboratory using urine at all applicable visits thereafter.

Estimated blood volumes are shown in [Section 6.1](#).

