## 6.2 DETAILS OF TRIAL PROCEDURES AT SELECTED VISITS

### 6.2.1 Screening period

#### Screening Period (Day -14)

Once the patient has provided informed consent (before any 1297.2 or 1297.3 trial-specific procedures or assessments are performed) and meets all inclusion criteria and none of the exclusion criteria (see [Section 3.3](#)), the trial site will enter the screened patient into the system using the Interactive Response Technology (IRT).

The following will also be performed/collected:

- Demographic information (including gender, date of birth, ethnicity and race), and medical and surgical history (including RA history and history of opportunistic infection)
- Evaluation of patient's willingness and ability to self-administer trial medication
- Physical examination, including height (cm) and weight (kg) (see [Section 5.3.1](#))
- Infection screen (HBsAg, HCV and HIV test, per the Investigator's discretion)
- Urine pregnancy test for women of child-bearing potential
- Patient questionnaires: global VAS, HAQ-DI and SF-36 v2 (see [Section 5.2](#))
- Joint assessment (see Section 5.2)
- TB test (QuantiFERON®-TB Gold test)
- ESR and CRP
- Physician questionnaire: global VAS (see Section 5.2)
- Vital signs (blood pressure, pulse rate, respiratory rate, and body temperature; see [Section 5.3.2](#))
- Laboratory testing (serum chemistry, hematology and urinalysis; see [Section 5.3.3](#))
- 12-lead ECG (see [Section 5.3.4](#))
- Previous and concomitant therapy (see [Section 4.2](#))
- Assessment of AEs (see [Section 5.3.6](#))

Once patients have signed the ICF, completed screening, and eligibility is confirmed, the Investigator will contact IRT and patients will be assigned to treatment with BI 695501. As part of the Trial 1297.2 Week 48 assessments, trial medication is administered. This is the last trial medication administration of the 1297.2 trial. During this visit, the Investigator/designee will train the patient on how to self-administer the trial medication. See [Section 4.1.4](#) for details.

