## **7.7 DETERMINATION OF SAMPLE SIZE**

All patients from the initial randomized controlled Trial 1297.2 willing and able to self-administer BI 695501 pre-filled syringe, and who are eligible for further treatment courses will be offered an additional treatment course with BI 695501. Patients are deemed eligible for further treatment courses if they have not experienced Investigator-reported drug-related SAEs during the 1297.2 trial, and in the Investigator's assessment can benefit from receiving BI 695501. It is anticipated that approximately 300 to 400 patients will be eligible to participate in this roll-over extension trial.

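### Section 2.3 promises to exclude patients with past HBV infection, but no criterion in Section 3.3.3 names past infection

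*Protocol*

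**What the plan says.** Section 2.3 describes HBV reactivation under anti-TNF therapy, notes that some cases were fatal, mostly in patients also taking other immunosuppressive drugs, and then gives the safeguard: "Carriers of HBV and patients with a history of HBV infection will be excluded from the trial".

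In Section 3.3.3 the only criterion that names HBV is criterion 8: "Positive serology for HBV or hepatitis C virus (HCV". It specifies no marker and does not mention history.

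The screening tests are described in three places, and all name the surface antigen as the HBV test:
- Flow Chart: "Infection screen: Hepatitis B (HbsAg); HCV and optional HIV test"
- Section 5.3.3: "patients must have a negative serological test for hepatitis B surface antigen (HBsAg), for hepatitis C serology"
- Section 6.2.1: "Infection screen (HBsAg, HCV and HIV test"

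Section 6.2.1 also collects "medical and surgical history (including RA history and history of opportunistic infection", without naming HBV.

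**The concern.** Section 2.3 tells ethics committees and regulators that two groups are kept out: HBV carriers and patients who have had HBV. Investigators enrol from the numbered list, and that list tells them to act on serology only. HBsAg shows current infection or carriage. It does not show resolved infection.

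The protocol itself gives reasons to care. Methotrexate is continued to Week 12 and oral corticosteroids are allowed up to 10 mg/day (Sections 3.1 and 4.2.2.1), so patients are on combined immunosuppression. No HBV test is scheduled after screening. SAP Section 16.1.10.1 tabulates HBV reactivation separately as one of the class safety topics.

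The gap would also go unrecorded. SAP Section 9.1 treats any departure from the inclusion or exclusion criteria as an important violation, but a patient with past HBV who breaches no numbered criterion would not be flagged.

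**Working it through.** The main check is a comparison of text. The only arithmetic is a bound on the number of patients.

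**1. What decides entry.** Section 3.3.4.1 bars anyone who fails an inclusion criterion or meets an exclusion criterion. Section 4.1.2 says that those who pass all of them are treated. Section 2.3 is not part of that rule.

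**2. Does any criterion require exclusion for past HBV?** All 4 inclusion and 26 exclusion criteria were read against a patient with known past HBV, negative HBsAg, no positive HBV serology on record and normal liver tests.

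| Criterion (Section 3.3.3) | What it covers | Excludes this patient? |
|---|---|---|
| 8 | Positive HBV or HCV serology | No: HBsAg is negative and no other HBV marker is ordered |
| 11 | Significant disease, in the investigator's opinion | Permitted, not required |
| 15 | Active infection, or infection recently treated | No |
| 16 | Serious or opportunistic infection during 1297.2 | No, if the infection came earlier |
| 21 | AST or ALT >1.5 × ULN | No |

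None of the 4 inclusion criteria and none of the 26 exclusion criteria names past HBV. Anti-HBs and HBV DNA appear only in the liver-injury work-up (Appendix 10.5), not at screening.

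**3. Does the list leave history to the parent trial?** Not in general. Criterion 3 reads "Primary or secondary immunodeficiency (history of, or currently active", and criterion 7 covers a history of cancer. Where history is meant for those conditions, the list says so.

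**4. How many patients.** Patients affected = N × p.
- N = 300 to 400, from Section 7.7: "It is anticipated that approximately 300 to 400 patients will be eligible to participate in this roll-over extension trial".
- p is the proportion with known past HBV, negative HBsAg and no positive serology on record. The documents do not give it, so the values below are assumptions.

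| Assumed p | N = 300 | N = 400 |
|---|---|---|
| 0% | 300 × 0 = 0 | 400 × 0 = 0 |
| 1% | 300 × 0.01 = 3 | 400 × 0.01 = 4 |
| 5% | 300 × 0.05 = 15 | 400 × 0.05 = 20 |

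**The case against.** The case on the other side has four parts.

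- **Criterion 8 is broader than HBsAg.** It names no marker, and Appendix 10.5 lists anti-HBs and DNA beside the surface antigen under its serology heading. A positive antibody result already on file could therefore trigger exclusion. This stands, and it narrows the gap to patients whose past infection is known but not backed by a positive serology result on record. It does not close the gap, because screening orders nothing that would produce such a result.

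- **The parent trial may have settled it.** Everyone must have completed 1297.2, and criteria 1, 6, 16, 17 and 19 look only at events or treatment in that trial. The infection criteria in particular ask about current tests, recent status and the 1297.2 period, which fits a roll-over list that takes earlier infection as already screened. This is plausible and could bring the number to zero. But the protocol does not say that 1297.2 excluded past HBV, and Section 2.3 states the exclusion for this trial.

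- **Risk is lower in these patients.** They have had 48 weeks of adalimumab or BI 695501, HBsAg is tested at the end of that period, HBV is among the serious infections for which treatment may be stopped, and liver tests continue. This reduces the expected harm. None of it excludes the patient.

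- **The 5% is unsupported.** True. It is an illustrative upper value for a joint condition and should not be read as an estimate.

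**Conclusion.** The inconsistency is real. A site that follows Section 3.3.3 exactly can enrol and treat a patient whom Section 2.3 says is excluded. The affected group is narrow: known past HBV, negative HBsAg and no positive HBV serology on record. Its size cannot be found from the documents. It is 0 if 1297.2 already excluded these patients, and 3 to 20 under assumed proportions of 1% to 5%.

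No estimate, analysis set or sample-size statement depends on it. The point should still be corrected, because the protocol offers this exclusion as its protection against a reaction that it says has been fatal in some cases. The main uncertainty is the eligibility criteria of 1297.2, which are not in the documents.

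**What to change.** Amend criterion 8 to read: *Known history of HBV infection, or positive serology for HBV or HCV.* Add HBV to the named items in the medical history taken at screening (Section 6.2.1), so that the criterion is checked against something recorded.

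If Trial 1297.2 already excluded past HBV, cite that exclusion in Sections 2.3 and 3.3.3 instead.

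The cost is one line in the criteria and one history prompt. Anti-HBc testing could be added but is not needed to make the two sections agree. No SAP analysis changes. The downside is that a few roll-over patients may become ineligible.
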